H1: EMR will improve functional and affective recovery to a greater extent than standard-of-care rehabilitation.

Explanation of H1: The purpose of H1 is to examine the effectiveness of EMR. If H1 is supported, this could establish EMR as the gold-standard practice for post-acute rehabilitation. Our primary analysis is the change from baseline to Day 30. This single primary endpoint allows for an effectiveness test that is not confounded by length of stay differences or post-discharge issues beyond the reach of EMR.

C2 Secondary Aim

Aim 2: Examine EMR's ability to overcome patient-level barriers to successful rehabilitation.

H2: The effectiveness of EMR for functional recovery will be greatest in: (a) patients with clinical depression; (b) patients with high levels of medical comorbidity; (c) patients with cognitive impairment.

Explanation of H2: EMR was designed to overcome barriers to rehabilitation (for example, due to depression); therefore, the difference in functional recovery between EMR and SOC should be greater in the most vulnerable older adults. If H2 is supported, we will demonstrate that older adults with these common comorbidities benefit the most from high intensity, high engagement rehabilitation. If so, this would refute conventional wisdom in post-acute rehabilitation, codified in admission criteria for rehabilitation facilities, regarding the appropriate candidates for rehabilitation (as described in Significance).³²

C3 Rationale for the Selection of Outcome Measures

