Outcomes	Function						
	Barthel Index (primary outcome)	X		X	X	X	X
	Gait speed	X		X	X		
	6-minute walk	X			X		
	Depression SCID (given if indicated by MADRS)	X					
	MADRS	X		X			
	17-item positive and negative affect scale	X	X	X		X	X
Processes	Rehabilitation intensity						
	Patient active time & actigraphy (at 20% of sessions at random)	collected each session throughout stay					
	Treatment engagement						
	Observer-rated Rehabilitation Participation Scale (at 20% of sessions at random)	collected each session throughout stay					
	Fidelity data (at 20% of session at random)	collected each session throughout stay					
	Post-Treatment Affect						
	Self-Assessment Moniker (at 20% of session at random)	collected each session throughout stay					
	Patient Satisfaction and Treatment Fidelity Survey	Collected after therapy sessions throughout stay					
	Other rehabilitation variables						
	Rehospitalization			X	X	X	X

Disposition (home, long-term care)	X		X	X	X	X
Social Participation (PROMIS Ability to Participate in Social Roles and Activities)					X	X
Instrumental Activities of Daily Living (OARS IADL)					X	X
Executive Functioning (Clock Drawing Test)	X					
Fear of Falling	X					
Readiness for Rehab	X	X				
Short Blessed Test	X					
Medical Comorbidity (CIRS-G)	X					
Barthel Index: Pre-morbid version	X					

F3 SNF Admit (Baseline) Visit

The baseline visit will take place immediately or soon after the patient consents to the study. The rater will conduct the following assessments: Barthel, 6 minute walk, gait speed, SCID, MADRS, PANAS, Disposition, Clock Drawing Test, Fear of Falling, Readiness for Rehab, CIRS-G, Barthel Index: Pre-morbid version.

F4 Day 7 Visit

The day 7 visit will take place 7 days after the patient consents to the study. The rater will conduct the following assessments: PANAS, Readiness for Rehab.

F5 Day 30 Visit

The day 30 visit will take place 30 days after the patient's date of admission to the facility. If the patient has already been discharged from the skilled nursing facility, the rater will call the patient to schedule a home visit to conduct the following assessments: Barthel, gait speed, MADRS, PANAS, Follow-up Disposition.

F6 SNF Discharge

The discharge visit will take place as close in time to the patient's discharge date as possible. The rater will conduct the following assessments at the skilled nursing facility: Barthel, 6 minute walk, gait speed, Discharge Location..

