F7 Day 60 Visit

The day 60 visit will take place 60 days after the patient's date of admission to the facility. Many participants will be discharged from the skilled nursing facility, but others will still be residing there. Unblinded research staff will determine where this assessment is to be conducted on a case-by-case basis depending on the patient's status. These assessments may be conducted over the phone depending on the patient's ability. The rater will conduct the following assessments: Barthel, PANAS, Follow-up Disposition, PROMIS Ability to Participate in Social Roles and Activities, OARS IADL.

F8 Day 90 Visit

The day 90 visit will take place 90 days after the patient's date of admission to the facility. Many participants will be discharged from the skilled nursing facility, but others will still be residing there. Unblinded research staff will determine where this assessment is to be conducted on a case-by-case basis depending on the patient's status. The rater will conduct the following assessments: Barthel, PANAS, Follow-up Disposition, PROMIS Ability to Participate in Social Roles and Activities, OARS IADL.

F9 Data and Safety Monitoring Plan

The Data Safety Monitoring Plan (DSMP) outlined below has been approved by the NIMH.

9.a General description of monitoring plan: This is a single-site study. [name] will be the primary monitoring entity. He will have primary responsibility for the monitoring of subjects during the entire time they participate in the study, both with respect to their safety (including confidentiality) and the integrity of their research data.

9.b Protection of Subject Privacy

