Explanation: The purpose of H1 is to examine the effectiveness of EMR. If H1 is supported, this could establish EMR as the gold-standard practice for post-acute rehabilitation. Our primary analysis is the change from baseline to Discharge. This single primary endpoint allows for an effectiveness test that is not confounded by length of stay differences or post-discharge issues beyond the reach of EMR.

2. Aim 2: Examine EMR's ability to overcome patient-level barriers to successful rehabilitation.

H2: The effectiveness of EMR for functional recovery will be greatest in: (a) patients with clinical depression; (b) patients with high levels of medical comorbidity; (c) patients with cognitive impairment.

Explanation: EMR was designed to overcome barriers to rehabilitation (for example, due to depression); therefore, the difference in functional recovery between EMR and SOC should be greater in the most vulnerable older adults. If H2 is supported, we will demonstrate that older adults with these common comorbidities benefit the most from high intensity, high engagement rehabilitation. If so, this would refute conventional wisdom in post-acute rehabilitation, codified in admission criteria for rehabilitation facilities, regarding the appropriate candidates for rehabilitation (as described in Significance).

3. Aim 3 (Secondary): Effect of EMR on MADRS scores on individuals with clinical depression.
4. Calculated a rate of clinical depression (SCID for those with elevated MADRS score):

22 participants had the SCID administered.

8 did not have depression diagnosis while 14 did have depression diagnosis.

Conclusion: only 14 individuals in the study had a clinical depression (ie, a diagnosis of depression). No further analyses to be done.

Additional Variables/Outcomes

6-Minute Walk/Gait Speed: Administered at Baseline and Discharge. Two components for 6-Minute Walk:

- 1) Distance Ambulated (feet): text box. If unable to complete, distance was entered as a 0.
- 2) Time: options are 6 minutes, Other time (MM:SS), and N/A

Two components for Gait Speed (Baseline, Day 30, Discharge):

- 1) Distance: radio button (10 meters, 4 meters, 0 meters). If unable, 0 meters selected.
- 2) Time (seconds): text box (if unable, time is 0).

Disposition (i.e., discharge to community vs. not)

Rehospitalization (rate).

Secondary analyses (not for main paper):

1. PANAS (A positive and a negative affect score).

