The primary measure employed for assessing functional improvement will be The Barthel Index. This index is a 10-item scale used to ascertain the degree of independence of normal daily activities. This will be done by taking the sum of these 10 items. A high score indicates a high degree of independence, and a score can range from 0 to 100.

- 2) Aim 2: Examine EMR's ability to overcome patient-level barriers to successful rehabilitation.

H2: The effectiveness of EMR for functional recovery will be greatest in: (a) patients with clinical depression; (b) patients with high levels of medical comorbidity; (c) patients with cognitive impairment.

Part (a) will be assessed using the MADRS, which is a 10-item scale used to assess for major depression. Each item is rated on a scale of 0 to 6, where a 6 is worse. The total score (i.e., sum of these 10 items) will be

used to assess for major depression and can range from 0 to 60.

Part (b) will be assessed using the CIRS-G, which is a 13-item scale used to assess for disease in all major body systems. Each item is rated on a scale of 0 to 4, with a 4 indicating severe impairment. The total score (i.e., sum of these 10 items) will be used to assess for medical comorbidity and can range from 0 to 52.

Part (c) will be assessed using the SBT Scores. The SBT is a 6-item scale used to assess for memory/concentration deficits. A total score, which is obtained after applying a weighting factor to each item then summing up the final item scores, can range from 0 to 28. A high score indicates impairment consistent with dementia.

ii. Analysis Methods

The primary outcome analysis for functional recovery will use a marginal model with time (baseline and discharge), condition (E-MR vs. SOC) and time x condition as fixed effects and with a covariance structure specified based on the Bayesian Information Criterion (BIC). Employing a marginal model allows for a more robust approach in the handling of missing data compared to the traditional ANCOVA model.

For H2 under Aim 2, each potential continuous moderator will be individually inserted into the primary model. The term of interest will be the time x condition x moderator interaction.

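### The SAP's primary endpoint, Barthel at SNF discharge, has no rule for participants transferred out or not discharged, and the two-row primary model leaves out the Day 30 Barthel that would help where it is missing

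*Protocol*

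**What the plan says.** The two documents name different primary time points. Protocol C1: "Our primary analysis is the change from baseline to Day 30". SAP Introduction ii (Objectives, Aim 1): "Our primary analysis is the change from baseline to Discharge". The SAP's measure is unambiguous (Analysis i): "The primary measure employed for assessing functional improvement will be The Barthel Index". Its primary model (Analysis ii) is a "marginal model with time (baseline and discharge), condition (E-MR vs. SOC) and time x condition as fixed effects", with the covariance structure chosen by BIC. Analysis iii relies on that model for missing data, without multiple imputation.

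The visit instructions are in the protocol. F6 asks for the discharge visit as near to the discharge date as can be managed and then says: "The rater will conduct the following assessments at the skilled nursing facility: Barthel, 6 minute walk, gait speed, Discharge Location". It gives no window and no other place or mode. For Day 30, F5 provides that if the participant has already left, "the rater will call the patient to schedule a home visit". F7 lets Day 60 be done by phone, and F7 and F8 leave the place of assessment to be decided case by case. Both also say: "Many participants will be discharged from the skilled nursing facility, but others will still be residing there". Protocol G4 expects transfers to other facilities and re-hospitalizations.

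The SAP's section on timing of assessments mentions windows in its title but gives none. Neither document defines discharge.

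**The concern.** Day 30 is a fixed date that every surviving participant reaches. Discharge is an event, and the instructions for measuring it were not extended when the SAP made it primary. Two groups fall outside them, for different reasons.

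- **Urgent transfer to hospital or another facility.** The participant may be gone before a rater can attend, and F6 offers no other place. Nothing says whether a later return to the SNF continues the index stay.
- **Still resident at Day 60 or Day 90.** Place is no obstacle here. What is missing is the triggering event, and the last scheduled visit is Day 90.

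Neither group has withdrawn, so the withdrawal rules do not cover them. For incapacity or death, protocol section 2.g seeks prognosis information from the chart or family, which is not a Barthel score. Both groups probably recover less well than those with a planned discharge. If their discharge Barthel is missing, the primary result depends on an untestable assumption, while a more informative measurement of the same scale, at Day 30, is left out of the model.

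**Working it through.** **1. What the primary model can use.** The schedule places the Barthel at baseline, Day 30, discharge, Day 60 and Day 90. The primary model has baseline and discharge rows only. A participant without a discharge value contributes a baseline value. Choosing the covariance by BIC implies a likelihood fit, so that value does inform the estimated discharge mean, through its correlation with discharge. The estimate is valid if, given baseline Barthel and arm, missingness is unrelated to the discharge score. Transfer because of deterioration after baseline makes that doubtful.

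**2. The plan's sample size.** Inputs from protocol G1: d = 0.4, 80% power, two-sided alpha 0.025; 1:1 allocation from section 2.d; N = 252 from the opening summary. Per arm, n = 2(z₀.₉₈₇₅ + z₀.₈₀)²/d² = 2(2.241 + 0.842)²/0.16, which rounds up to 119, so N = 238; the t-based figure is 242. The planned 252 is slightly more than its inputs need, with power 0.825 (normal) or 0.821 (t). The reserve is small.

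**3. Power if discharge values are missing.** The documents give no rate, so the rates are assumed. Power = Φ(d√(n/2) − z), with n = 126 × (1 − share missing). Participants without a discharge value are counted as adding nothing, which slightly overstates the loss.

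| Assumed share missing | Discharge values | Power, alpha 0.025 | Power, alpha 0.05 (SAP level) |
|---|---|---|---|
| 0% | 252 | 0.825 | 0.888 |
| 5% | 239 | 0.803 | 0.872 |
| 10% | 227 | 0.780 | 0.854 |
| 20% | 202 | 0.725 | 0.811 |

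**4. Bias.** Suppose participants without a discharge value lie g SD below the others in both arms, with missingness unrelated to baseline. The observed difference then shifts by g × (share missing in EMR − share missing in SOC). With g assumed at 0.5-1.5 and shares differing by 5-10 percentage points, the shift runs from 0.5 × 0.05 = 0.025 SD to 1.5 × 0.10 = 0.15 SD, in either direction. The upper end is 0.15/0.4 = 38% of the design effect. With equal shares and equal g, it is zero.

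**5. What a Day 30 row could recover (all figures assumed).** Take a mean Barthel gain of 30 points with a discharge value and 10 without, in both arms, and 10% (EMR) v 20% (SOC) without one. Full means are 0.9×30 + 0.1×10 = 28 and 0.8×30 + 0.2×10 = 26, a difference of 2. The two-row model, with missingness unrelated to baseline, gives 30 − 30 = 0. Now add Day 30, supposing that the 20-point deficit is already present then, that Day 30 is observed for these participants, and that the slope of discharge on Day 30 is 0.6-0.8. The estimated difference is slope × 20 × (0.20 − 0.10) = 1.2 to 1.6 points. For 15% v 20%, the full difference is 27 − 26 = 1 and the recovered part is slope × 20 × 0.05 = 0.6 to 0.8. The zero in the two-row model is built in by giving both arms the same gain. The example shows the mechanism and does not estimate the trial's bias.

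**The case against.** Much can be said for the plan as it stands.

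- F6 names the SNF but does not forbid another place, and its loose timing allows an assessment shortly before a planned discharge. A reader might infer that anyone transferred or not discharged necessarily has no primary value because of the location rule. The text does not go that far, and location does not explain the participants who stay.
- A reader might infer that the two-row model gains nothing from a participant with only a baseline value. Step 1 shows otherwise. The narrower criticism, that it relies on baseline and arm alone, stands.
- A reader might infer that any EMR benefit through fewer rehospitalizations or more returns home drops out of the primary comparison. The documents do not support this: rates and deficits are unknown, the bias has no fixed sign, and a planned discharge to long-term care is still a discharge.
- The affected groups may be small. The protocol excludes patients in whom early re-hospitalization is expected and those who normally live in long-term care, and gives a usual stay of about 3 weeks. G4's remark on transfers concerns follow-up to Day 90, not specifically events before discharge.
- The SAP's CONSORT list already counts attendance at each visit, including discharge, with reasons for loss. Rehospitalization is tested separately, and self-reported function is modelled at Days 30, 60 and 90.

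These points limit the size of the concern and most of the reporting request. They do not supply a definition of discharge, a rule for the two groups, or a reason to leave Day 30 out of the model.

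**Conclusion.** The gap is real: an event-triggered primary endpoint, no definition of the event, no rule for two groups the protocol expects, and a model whose validity rests on baseline Barthel and arm. Its size cannot be derived from the documents. If 10-20% of discharge values were missing, power would be 0.78-0.73 at alpha 0.025, or 0.85-0.81 at the SAP's 5% level. Bias could run in either direction or be nil. The documents do not show that the primary result is biased, or that EMR is disadvantaged. What they do support is a low-cost improvement to the primary model, because a more informative Barthel value is already scheduled.

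**What to change.** In SAP Analysis ii, add the Day 30 Barthel as a further categorical time row in the marginal model, with an unstructured covariance matrix. Keep the baseline-to-discharge time x condition contrast as the primary estimate. At minimum, prespecify this as a sensitivity analysis. Unstructured is preferable to a structure that assumes ordered visits, because Day 30 falls after discharge for a typical 3-week stay and before it for a long one. For that reason Day 30 should serve as auxiliary information and not stand in for a discharge value. Nor should the last Barthel by Day 90 be substituted: it mixes measurement times and, since Day 60 may be by phone, possibly modes.

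Define discharge in the SAP and state whether a return after hospital transfer continues the index stay. Break down the planned CONSORT count for the discharge visit by arm and reason: unplanned transfer, or not discharged by Day 90.

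The cost is a few lines of SAP text and one more row per participant; no new data are needed. Day 30 will not help everyone, since F5 provides only a home visit for those who have left and a participant in hospital that day may be missed. Amend F6 to allow off-site assessment only if data collection is still open. The SAP already gives SCID totals and describes trial conduct in the past tense, so it probably is not.

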EMR group: The EMR group will be the same as in our pilot study; participants who are randomized to the EMR group will receive therapy only from therapists who are trained and supervised in EMR. Their therapy sessions will follow the EMR protocol. Otherwise their SNF care will not differ from usual care.

SOC group: The standard-of-care (SOC) group will receive therapy only from PT/OTs (or assistants) who are not trained nor supervised in EMR. These therapists are monitored (videotaped or observed) but not asked to do anything differently with their patients.

Blinding: Ratings will be conducted by a research associate who is blind to the study intervention, purpose, and randomization status. Patients will not be blinded to their randomization status, but will not be made knowledgeable about how exactly Enhanced Rehab is different from SOC. Therapists providing SOC treatment will be blinded to the principles of Enhanced Rehab to prevent contamination.

Open Label participants: Up to 12 participants at each site will be recruited as "open label pilot" participants. These participants will meet the same eligibility criteria as the randomized participants but will be automatically assigned to the Enhanced group. This will be done prior to beginning to randomize participants to ensure the quality of the intervention and data collection procedures.

2.e Risks and Benefits

Likely risks: There are no likely risks.

Less Likely risks: The enhanced rehabilitation intervention and the measures impose some risk of emotional discomfort. The enhanced rehabilitation may cause muscle soreness and fatigue. If patients are allowed to take Tylenol or NSAID they may do so with approval from their skilled nursing home doctor.

Rare risks: There is a potential breach of confidentiality with research records and with videotaping. There is a possibility of falling and fracture during the tests of your walking and balance. This will be minimized through the use of a safety belt during all testing procedures

Benefits: Research assessments may reveal conditions that had not been identified (e.g., depression), leading to management of the patients' depression or functional recovery that would not have occurred otherwise. Research intervention (i.e., Enhanced

Rehab) may lead to improvements in physical functioning (compared to standard of care).

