addition, we recognize that medically ill and debilitated older adults can easily feel overwhelmed or fatigued by what would be minimally demanding tasks for others. Therefore, we include this discomfort in the potential risks. The instruments to be used in this study have been used by the PI in other studies of older medically ill and disabled adults. There are very few older adults who are unable to tolerate the length of the questionnaires. If this occurs, an assessment battery can be divided into several sessions.

Enhanced Medical Rehabilitation: Participants assigned to Enhanced Medical Rehabilitation will receive a higher intensity of therapy. This has the theoretical risk of causing cardiac events (as does any rehabilitation). Only trained physical and occupational therapists (and assistants), who are well-trained in the assessment of cardiac concerns during rehabilitation, will work with the participants.

Because this study involves participants with depression, there is a risk of suicidal behavior. However, these are risks associated with the illness not the study.

Risks in relation to benefits: No subjects will be denied interventions; participants receive either the standard of care rehabilitation, or Enhanced Medical Rehabilitation. No risks other than possible emotional distress exist from the study assessments. Thus, the risks involved in participating in this study are deemed low, which justifies the data and safety monitoring plan described here.

9.g Data Collection Procedures for Adverse Events

We will systematically collect AEs and summarize them in a running table throughout the study, including date of onset/offset, type of AE, severity, and interventions if any. Per Washington University IRB policy, reportable AEs are those that are possibly, probably, or definitely related to the study intervention or procedures.

9.h Reporting Procedures

SAEs that are unanticipated, serious, and possibly related to the study intervention will be reported to the IRB, and NIMH in accordance with requirements.

- Unexpected fatal or life-threatening AEs related to the intervention will be reported to the NIMH Program Officer within 7 days. Other serious and unexpected AEs related to the intervention will be reported to the NIMH Program Official within 15 days.
- Anticipated SAEs will be handled in a less urgent manner but will be reported to the IRB in accordance with their requirements.

G Statistical Plan

G1 Sample Size Determination and Power

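### The NIMH reporting triggers in 9.h and the SAP omit events related to study procedures, so a serious fall or fracture in a research walking test misses the 7- and 15-day reports, and the monitoring plan denies a risk that 2.e names.

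*Protocol*

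**What the plan says.** **Collection and attribution.** Under Protocol 9.f i, each AE is classified by its likely relation to the intervention or to other study procedures. Section 9.g, citing the university's IRB policy, says that "reportable AEs are those that are possibly, probably, or definitely related to the study intervention or procedures". It also keeps a running table of all AEs.

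**Reporting to NIMH.** Section 9.h opens with "SAEs that are unanticipated, serious, and possibly related to the study intervention will be reported to the IRB, and NIMH in accordance with requirements". Two timed rules follow: "Unexpected fatal or life-threatening AEs related to the intervention will be reported to the NIMH Program Officer within 7 days" and "Other serious and unexpected AEs related to the intervention will be reported to the NIMH Program Official within 15 days". For the rest, "Anticipated SAEs will be handled in a less urgent manner" and go to the IRB; NIMH is not named there. The SAP Harms section repeats both the wide attribution scale and the narrow triggers.

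**Risks of the assessments.** Protocol 2.e lists among the rare risks: "There is a possibility of falling and fracture during the tests of your walking and balance". It adds that a safety belt will be used to reduce this. In the monitoring plan, 9.f iii (Expected Risks) says instead: "No risks other than possible emotional distress exist from the study assessments". The next sentence concludes that the risks are low and that this justifies the monitoring plan.

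**The concern.** Relation to study procedures is recorded and makes an event reportable in 9.f i and 9.g, then disappears from every sentence that sends an event to NIMH. The physical harm that the protocol links to its own assessments is a fall or fracture in a walking test. That harm comes from a procedure, not from the intervention.

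At stake is whether the funder, which approved the monitoring plan, hears promptly of serious injuries caused by research testing in frail older adults. The written triggers carry weight here: 9.a names one individual as the primary monitoring entity, and I1 says there is no additional monitoring. The plan's stated reason for its level of monitoring also leaves out the risk that 2.e discloses.

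**Working it through.** This is a check of text. The plan states no figure to reproduce.

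**Step 1. Scope of each rule.**

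| Place | Relation covered | Recipient |
|---|---|---|
| 9.f i, attribution scale | intervention or procedures | recorded for every AE |
| 9.g, reportable AEs | intervention or procedures; possibly, probably or definitely | IRB (university policy) |
| 9.h, lead sentence | intervention only; possibly related | IRB and NIMH |
| 9.h, 7-day rule | intervention only; related | NIMH |
| 9.h, 15-day rule | intervention only; related | NIMH |
| 9.h, anticipated SAEs | not stated | IRB |
| SAP Harms, attribution | intervention or procedures | recorded for every AE |
| SAP Harms, triggers | intervention only | as 9.h |

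Within 9.h the degree of relation also shifts: the lead sentence accepts a possible relation, while the timed rules say only that the event is related.

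**Step 2. Apply the rules to one event.** Take a fracture during gait-speed or six-minute-walk testing that leads to hospital admission.

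- *Serious?* Yes. Inpatient hospitalization meets the SAE definition in 9.e.
- *Related to the intervention?* No. F3, F5 and F6 assign these tests to the rater, and they are not part of EMR therapy. Standard-of-care participants take the same tests without receiving EMR, so for them no relation to EMR can be argued.
- *Related to a procedure?* Yes, so 9.g makes it reportable to the IRB.
- *7-day or 15-day NIMH report?* Neither. The event fails on relation, whether or not it counts as expected.

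**Step 3. Exposure.** The schedule gives gait speed at baseline, Day 30 and discharge (3) and the six-minute walk at baseline and discharge (2). That is 3 + 2 = 5 tests per participant. For the planned 252 participants, 5 × 252 = 1,260 tests. This is a ceiling: not everyone completes every test, and the SAP provides zero entries for those unable. The Day 30 gait test takes place at a home visit if the participant has been discharged (F5). Neither document gives a fall or fracture rate, so no event count follows.

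**Step 4. Compare the risk statements.** Section 2.e names falls and fracture from the walking and balance tests. Section 9.f iii says the assessments carry no risk but emotional distress. Both cannot stand. The 9.f iii sentence also disagrees with its own section, which lists breach of confidentiality and fatigue as risks of the assessments.

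**Step 5. Expectedness.** Section 9.h turns on whether an event is unanticipated or unexpected, and neither term is defined. Whether a test-related fracture is anticipated depends on whether 2.e or 9.f iii is read. The same gap affects cardiac events in EMR: 9.f iii places them under Expected Risks but calls the risk theoretical, and no sentence says that this section decides expectedness under 9.h.

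**The case against.** The strongest reply is that the rules serve different recipients. The 9.g sentence states IRB policy, and the timed rules in 9.h concern NIMH. Different scopes for different bodies are not in themselves a contradiction. NIMH approved the plan, its own requirements are not in the documents, and limiting expedited reports to unexpected events is a legitimate choice. All of this stands. It does not explain why relation to procedures is recorded for every AE and then left out of every NIMH trigger, with no reason given, when 2.e names a procedure-related injury.

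A reader might infer that these injuries escape all reporting. The documents do not support that. Such an event is recorded in the running AE table, attributed, and reportable to the IRB under 9.g, and anticipated SAEs also go to the IRB. Section 9.d mentions annual summaries without naming a recipient, so it cannot be said that NIMH would never learn of them.

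A reader might also infer that every cardiac event in EMR, even a fatal one, is excluded from the 7-day rule. That rests on a sub-heading in a narrative section, with the key term undefined and the risk called theoretical. An investigator could judge a given event unexpected. This is an ambiguity, not an established exclusion.

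Finally, 2.e classes falls and fracture as rare and mitigated, which is compatible with an overall judgement of low risk. The contradiction lies in the sentence denying the risk; it does not show that the level of monitoring is wrong.

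**Conclusion.** The point holds for expedited reporting to NIMH. On the plain wording of 9.h and SAP Harms, a serious fall or fracture in a research walking test reaches the IRB but is outside both the 7-day and the 15-day NIMH report, in either arm. The monitoring plan's denial of any assessment risk beyond emotional distress contradicts 2.e and should not be part of the justification for the plan.

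The conclusion rests on two readings: that the intervention in 9.h means EMR and not the research assessments, as the separate mention of procedures in 9.f i and 9.g implies, and that the rater-run walking tests are study procedures. It needs no assumed fall rate. The size is a gap in which events reach the funder on time, over up to five tests per participant; the number of events cannot be stated. It has no bearing on the treatment estimate or its error rates. It is worth correcting on safety grounds because the change is small.

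**What to change.** 1. In 9.h (the lead sentence and both timed rules) and in SAP Harms, replace the relation clause with the scope of 9.g, so that the triggers cover events judged possibly, probably or definitely related to the intervention or to study procedures. This also removes the shift in degree of relation within 9.h.
2. In 9.f iii, delete or correct the sentence that denies other assessment risks, and name falls and fracture in walking tests so that the section agrees with 2.e. Restate the justification for the monitoring level with that risk included.
3. State that naming a risk in 2.e or 9.f iii does not by itself make an event anticipated or expected under 9.h. Without this, step 2 could move test-related fractures outside the timed rules on expectedness. The same sentence settles the ambiguity for cardiac events in EMR.

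The cost is a wording amendment to the monitoring plan and the SAP, which would presumably go back to NIMH because the plan is described as NIMH-approved, and a few more expedited reports. Relation to procedures is already recorded for each AE, so no new data are needed.
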